Health effects of Biostimulants lettuce in Human (NUTRIWEED23)

Unique protocol ID Weed2023

07/12/2023

The aim of the project is to study the influence of Biostimulants Lettuce crops on a healthy population in order to assess influence on hematological parameters and specific metabolism (glucose, lipid, iron, bone) and gut and lipid hormones. Secondary outcome will be to find out micronutrient presence in urine and serum in order to evaluate vegetables as biocarrier. The use of biostimulants in modern agriculture has rapidly expanded in recent years, owing to their beneficial effects on crop yield and product quality, which have come under the scope of intensive research.

The present project aims to investigate the benefits of biostimulants lettuce in a cohort of healthy individuals. Biostimulants are organic and inorganic compounds or microorganisms that when applied to plants can enhance plants' growth, yield, and tolerance to stress. Specifically, participants will be fed with biostimulated lettuce in order to study the influence on hematological parameters.

The healthy group will eat 100 grams of Lettuce (control group) and 100 grams of Biostimulated lettuce (intervention group) with weed or saline and collect plasma and urine samples after 15 days. Each subject will be subjected to two venous blood samples taken at the beginning of the observation and at the end. The samples obtained will be transported in certified containers for the safe transport of biological samples, and, subsequently, processed by the experimenters at the laboratories of the Molecular Biology section of the University of Palermo. Serum and plasma will be obtained from each blood sample. All information thus obtained will be recorded in a database in which each person will be identified with a numerical code, in order to comply with current privacy regulations. Body weight, Barefoot standing height, Body mass index, Body composition will be measured in the different groups of study. Samples will be analyzed and compared for glucose, albumin, total cholesterol, HDL-cholesterol, LDL-cholesterol, triglycerides, uric acid, creatinine, AST, ALT, γ -GT, ALP, bilirubin, Ferritin, free Iron, transferrin, total proteins, Magnesium, Calcium, insulin, osteocalcin, hematocrit, hs-CRP, TSH, FT3, FT4. Bone metabolism (Osteocalcin, parathyroid hormone, CTX, Calcitonin), Vitamin D Calcium, Phosphate, Potassium, gastric hormones (GIP, GLP1, GLP2, ghrelin, glucagon, PYY, CCK, leptin, resistin). The Outcome Measures will be Body weight, Barefoot standing height, Body mass index, Body composition by impedance analysis will be measured in the groups of study. Blood samples will be collected from the different groups of study and will be analyzed for glucose, albumin, total cholesterol, HDL-cholesterol, LDL-cholesterol, triglycerides, uric acid, creatinine, AST, ALT, γ -GT, ALP, bilirubin, Ferritin, free Iron, transferrin, total proteins, Magnesium, Calcium, insulin, osteocalcin, hematocrit, hs-CRP, TSH, FT3, FT4. Bone metabolism (Osteocalcin, parathyroid hormone, CTX, Calcitonin), Vitamin D Calcium, Phosphate, Potassium, gastric hormones (GIP, GLP1, GLP2, ghrelin, glucagon, PYY, CCK, leptin, resistin)

Statistical analysis plan:

Student t tests will be used to compare the baseline characteristics of the two groups. Changes between baseline and follow-up will be analyzed by one-way ANOVA followed by Tukey's posttest. A $P < 0.05$ will be considered to be statistically significant by using appropriate software.

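### Allocation and masking are unstated, so neither change scores nor ANCOVA is safe by default; if allocation is random, ANCOVA on the planned baseline blood value is usually more precise than ANOVA of changes

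*Combined protocol and SAP*

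**What the plan says.** The Combined protocol and SAP has no numbered sections. The study-procedures text states that "The healthy group will eat 100 grams of Lettuce (control group) and 100 grams of Biostimulated lettuce (intervention group) with weed or saline". It gives no method of assignment, no sequence, no concealment and no masking.

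On measurement: "Each subject will be subjected to two venous blood samples taken at the beginning of the observation and at the end". A separate phrase says the study will "collect plasma and urine samples after 15 days". The aim adds: "Secondary outcome will be to find out micronutrient presence in urine and serum". For anthropometry: "Body weight, Barefoot standing height, Body mass index, Body composition will be measured in the different groups of study", with no time given.

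On handling, samples are "processed by the experimenters at the laboratories of the Molecular Biology section". In the database, "each person will be identified with a numerical code, in order to comply with current privacy regulations"; no other purpose is given for the code.

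Under the heading Statistical analysis plan, baseline characteristics of two groups are compared by t test. Then: "Changes between baseline and follow-up will be analyzed by one-way ANOVA followed by Tukey's posttest". Significance is P < 0.05. There is no baseline covariate, no confounder adjustment and no sample size.

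**The concern.** The stated aim is causal: the influence and benefits of biostimulated lettuce. Whether a difference between groups can be read that way depends first on how the groups were formed, and the text does not say. The right analysis depends on the same fact. With random allocation, baseline differences are chance, and using the baseline as a covariate normally sharpens the comparison. Without it, change scores and ANCOVA rest on different assumptions about how the groups would have evolved, and each can produce a false effect where the other does not. The plan also leaves a planned baseline blood value out of the model, which may waste information in what could be a small study.

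**Working it through.** **Inputs.** From the documents: a control and an intervention group, blood at start and end, ANOVA of changes, P < 0.05. The documents give no n, SD or correlation, so there is no figure of the plan's own to reproduce. Assumed: two parallel groups of n each, SD 1 at both times within group, baseline to follow-up correlation r of 0.5, 0.7 or 0.9, two-sided 5%.

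**1. Precision under random allocation (large sample).** In units of 2·SD²/n, Var(change) = 2(1 − r) and Var(ANCOVA) = 1 − r². The ratio is (1 − r²)/[2(1 − r)] = (1 + r)/2.
- r = 0.5: 0.75/1.00 = 0.75
- r = 0.7: 0.51/0.60 = 0.85
- r = 0.9: 0.19/0.20 = 0.95

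Inverting, the change analysis needs about 33%, 18% and 5% more participants. For a true 0.5 SD effect with 30 per group, power (change v ANCOVA) is 48% v 59%, 69% v 75% and 99% v 99%.

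**2. Small groups.** Estimating the slope multiplies the ANCOVA variance by 1 + 1/(2n − 4). The gain is gone once r exceeds 2/[1 + 1/(2n − 4)] − 1.
- n = 6: factor 1.125, break-even r = 0.78; ratio at r = 0.9 is 0.95 × 1.125 = 1.069
- n = 10: factor 1.0625, break-even r = 0.88; ratio at r = 0.9 is 0.95 × 1.0625 = 1.009 (simulated 1.007)
- n = 20: break-even r = 0.95
- n = 50: break-even r = 0.98

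At n = 6 the ratio is still 0.84 at r = 0.5 and 0.96 at r = 0.7.

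**3. Validity under random allocation.** In simulation with no true effect (40,000 runs per cell, n = 15 to 50), both tests rejected in 4.8–5.2% of runs.

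**4. Chance imbalance under random allocation.** Take an observed baseline imbalance of exactly 0.5 SD and r = 0.5. The change test then rejects 7.2% at n = 15 and 20.5% at n = 50. The probability of an imbalance at least that large, 2[1 − Φ(0.5/√(2/n))], runs the other way: 17% at n = 15 and 1.2% at n = 50.

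**5. Non-random allocation, baseline difference 0.5 SD, no true effect.**
- The groups differ stably: change is unbiased, and ANCOVA is biased by (1 − r) × 0.5, which is 0.15 SD at r = 0.7 (simulated 0.152). ANCOVA rejects 11–28%, 8–17% and 6–9% at r = 0.5, 0.7 and 0.9 (n = 15 to 50); change stays near 5%.
- Both groups regress to a common mean: ANCOVA is unbiased, and change is biased by −(1 − r) × 0.5, which is −0.15 SD at r = 0.7. Change rejects 10–24%, 8–16% and 6–9%; ANCOVA stays near 5%.

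**6. Does the baseline t test settle it?** No. Its power to detect a 0.5 SD imbalance is 20%, 35% and 49% at 10, 20 and 30 per group.

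**The case against.** The strongest reply is that under random allocation the planned test is already valid, so ANCOVA is an efficiency preference whose value depends on an assumed r. That stands. At r = 0.9 the gain is negligible, and in very small groups it can reverse. A reader might infer that ANCOVA is always the more precise choice; with no n stated, the documents do not support that.

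Other inferences also go too far:
- *That allocation is non-random or the laboratory unmasked.* The text is silent on allocation. Processing by the experimenters does not show that they know the group, and a code given for privacy does not show that they do not. Laboratory bias is plausible, but nothing here allows it to be sized.
- *That chance imbalance pushes the error rate to about 21%.* That figure is conditional on an imbalance with probability 1.2% at that group size. Overall the test holds 5%.
- *That urine and body measures have no baseline.* The phrase about collection after 15 days also covers plasma, which is obtained from both blood samples, so it is not a complete schedule. The SAP speaks of changes without limiting this to blood. Timing is unclear, not shown to be absent.

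Finally, the arithmetic fits only a parallel two-group design. The baseline t-test sentence supports that reading. The weed-or-saline phrase and the Tukey test may point to more groups, and the opening sentence could be read as one group eating both lettuces. If the ANOVA is instead run over group-by-time cells, it ignores pairing, and the figures above do not describe it.

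**Conclusion.** The concern holds, with limits. What is firm is that allocation and masking are not stated in the text supplied, and that without random allocation neither change scores nor ANCOVA protects against reading a pre-existing difference as an effect. With an assumed 0.5 SD difference and 15 to 50 per group, whichever method's assumption fails rejects about 6–28% of the time, against a nominal 5%.

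The ANCOVA part is conditional. Given random allocation, equal SDs and two parallel groups, it cuts variance by 25%, 15% or 5% at r = 0.5, 0.7 or 0.9 in large samples, with little or nothing to gain for very stable outcomes in very small groups. It is an improvement in precision, not the repair of an invalid test. The allocation omission carries the weight of the point.

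**What to change.** 1. State how participants are allocated and who is masked. If they are not yet assigned, allocate from a pre-generated, concealed random list linked to the existing numerical code, and give the laboratory coded samples only.
2. With random allocation, analyse each blood outcome by ANCOVA: follow-up value on group and that outcome's own baseline. Use Tukey-adjusted contrasts only if there are more than two groups.
3. If allocation was not random, say so. Name one primary analysis in advance, with the assumption it rests on, and keep the other as sensitivity; two results per analyte with neither primary would invite selection. Word conclusions as association.
4. State whether urine and body measures are taken at baseline. If so, use the same ANCOVA; if not, compare follow-up values only.
5. Reconcile the weed-or-saline phrase and the Tukey test with the two groups named in the SAP.

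Cost: a small set-up task for the list and labels, a few lines of text, and one residual degree of freedom per model. The blood ANCOVA needs no new data, since both samples are planned. If people are already assigned, coded labels can still be used for samples not yet assayed.

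### One-way ANOVA on change is valid for two groups, but under randomised allocation it is modestly less precise than ANCOVA on the scheduled baseline blood value, and the Tukey step is redundant

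*Combined protocol and SAP*

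**What the plan says.** Under the heading Statistical analysis plan, the efficacy analysis is one sentence, which begins "Changes between baseline and follow-up will be analyzed by one-way ANOVA followed by Tukey" and names Tukey's procedure as the post-test. The sentence before it sets the number of groups: "Student t tests will be used to compare the baseline characteristics of the two groups". No baseline covariate, effect estimate or confidence interval is mentioned.

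The study procedures paragraph gives the arms: "The healthy group will eat 100 grams of Lettuce (control group) and 100 grams of Biostimulated lettuce (intervention group) with weed or saline". It also schedules the blood draws: "Each subject will be subjected to two venous blood samples taken at the beginning of the observation and at the end". A baseline blood value is therefore planned for every participant. Urine is mentioned only after 15 days, and the body measurements have no stated time.

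The documents do not say whether allocation is randomised. They give no sample size, standard deviation, expected difference or correlation between the two measurements.

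**The concern.** A change score subtracts the whole baseline value from the follow-up value, which amounts to fixing the baseline slope at 1. When SDs are equal at the two times, the slope that best predicts follow-up is rho. The further rho lies below 1, the more baseline noise the change score carries into the comparison. Under randomisation, ANCOVA estimates the slope from the data and targets the same group effect with less variance.

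What is at stake is precision, not validity: wider intervals and lower power than the scheduled blood samples could give. Tukey's post-test also has no work to do if there are only two groups.

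**Working it through.** **Inputs.** From the documents: two groups (SAP), blood at start and end (study procedures), significance at P < 0.05 (SAP; taken as two-sided). Assumed, because the documents give none: equal arms with n per arm of 10, 20 or 40; equal SDs at both times and in both arms; rho of 0.5, 0.7 or 0.9; for power, a true difference of 0.5 SD. There is no sample-size figure in the plan to reproduce.

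**1. Two groups: what the stated test is.** One-way ANOVA of individual change by group gives F = t². The Tukey critical value divided by √2 equals the t critical value; at n = 20 per arm (38 df) both are 2.0244. On one generated data set of that size, the t test, ANOVA and Tukey p-values were all 0.1360. In simulation with no effect (4,000 runs per setting; n = 10, 20 and 30 per arm), the change-score test rejected in 4.7% to 5.7% of runs and ANCOVA in 4.6% to 5.4%. Both are consistent with 5%.

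**2. Variance of the group effect under randomisation** (units of SD²):

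- Change score: (2/n) × 2(1 − rho)
- ANCOVA, normal random covariate: (2/n) × (1 − rho²) × (1 + 1/(2n − 4))
- Ratio, change score to ANCOVA: 2/(1 + rho) × (2n − 4)/(2n − 3)

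At n = 20 per arm, 2/n = 0.1, 1 + 1/36 = 1.0278 and 36/37 = 0.973:

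| rho | Change score | ANCOVA | Ratio |
|---|---|---|---|
| 0.5 | 0.1 × 1.0 = 0.1000 | 0.1 × 0.75 × 1.0278 = 0.0771 | 1.333 × 0.973 = 1.30 |
| 0.7 | 0.1 × 0.6 = 0.0600 | 0.1 × 0.51 × 1.0278 = 0.0524 | 1.176 × 0.973 = 1.14 |
| 0.9 | 0.1 × 0.2 = 0.0200 | 0.1 × 0.19 × 1.0278 = 0.0195 | 1.053 × 0.973 = 1.02 |

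The same formula gives 1.25, 1.11 and 0.99 at n = 10 (factor 16/17), and 1.32, 1.16 and 1.04 at n = 40 (factor 76/77). A simulation of 100,000 replicates gave 1.26/1.10/0.99, 1.30/1.15/1.03 and 1.32/1.16/1.04 at n = 10, 20 and 40, within about 0.01 of the formula.

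**3. Where the gain ends.** Setting the ratio to 1 gives rho = 2(2n − 4)/(2n − 3) − 1. That is 0.88 at n = 10 and 0.95 at n = 20 per arm.

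**4. What it means for the reader of a result** (rho 0.5/0.7/0.9):

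- Power, change score against ANCOVA: n = 10, 19/28/66% against 22/30/65%; n = 20, 34/51/93% against 42/57/94%; n = 40, 60/81/>99% against 72/87/>99%.
- Mean 95% CI half-width at n = 20: 0.64/0.49/0.28 SD against 0.56/0.46/0.28 SD.

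**5. Why the advice depends on randomisation.** Suppose there is no effect but the arms differ by 0.5 SD at baseline (50,000 replicates, n = 20 per arm).

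- If the difference persists, ANCOVA is biased by (1 − rho) × 0.5 = 0.25/0.15/0.05 SD and rejects in 14/10/7% of runs; the change score stays near 5%.
- If the difference regresses to a common mean, the change score has a bias of the same size with opposite sign and rejects in 12/9/7%; ANCOVA stays near 5%.

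Without randomisation, then, neither method is safe in general.

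**The case against.** The strongest answer is that the plan's test is valid, so preferring ANCOVA is a matter of efficiency. It also rests on a condition the documents do not supply: if allocation is not randomised, the change score remains a reasonable main analysis. Even with randomisation the gain can be nil, since at 10 per arm and rho 0.9 the ratio is 0.99. All of this stands, and it limits the weight of the point. It does not remove it: at rho of 0.5 to 0.7 the gain is real and needs no extra samples.

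Stronger readings are tempting, and the documents do not support them:

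- **That the efficacy analysis is undefined or invalid because no factor or contrast is named.** Group is the only factor described, and the control and intervention arms are labelled. The absent estimate and confidence interval are missing detail.
- **That ANOVA and Tukey would be run on four group-by-time cells, ignoring pairing.** The sentence analyses changes, and a change is one value per participant. A four-cell analysis contains no changes.
- **That there are three or more arms.** The weed-or-saline phrase is unclear, but it does not clearly add an arm. Referring to different groups, as in "Blood samples will be collected from the different groups of study", is compatible with two. If there were more than two arms, Tukey on the changes would be proper.

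With two arms Tukey is redundant but harmless: it changes no p-value.

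**Conclusion.** The point holds in a limited form, and its severity is minor. One-way ANOVA on individual change is a valid comparison of the two groups. If allocation is randomised, it is less precise than ANCOVA on the baseline blood value. At an assumed 20 per arm, the excess variance is about 30% at rho 0.5, 14% at rho 0.7 and 2% at rho 0.9. These figures assume two equal arms and equal SDs. The correlation may differ between analytes, so the gain may too. The claim covers blood outcomes only, because a baseline value is documented only for blood.

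**What to change.** State whether allocation is randomised, then choose the text accordingly.

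- **If randomised**, replace the efficacy sentence with: *For each blood outcome measured at baseline and day 15, the day-15 value will be compared between groups by ANCOVA with group as factor and baseline value as covariate; the adjusted between-group difference with 95% CI is the effect estimate.*
- **If not randomised**, keep the between-group difference in individual change as the main estimate, with its 95% CI, and report ANCOVA as a sensitivity analysis. Name the main estimate before data are examined.

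Drop Tukey's post-test unless there are three or more arms. Reconcile the weed-or-saline phrase in the study procedures with the two groups in the SAP.

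The cost is a few sentences and one more model term per outcome, with no added blood sampling. The drawbacks are that ANCOVA gains nothing at high rho or in a very small trial, and that its advantage depends on randomisation.

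### One analysis of change for every marker, with no transformation or baseline adjustment, loses power on strongly right-skewed markers; a short pre-fixed log list with ANCOVA recovers it

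*Combined protocol and SAP*

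**What the plan says.** The Statistical analysis plan, at the end of the combined document, has three sentences.

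- Baseline: "Student t tests will be used to compare the baseline characteristics of the two groups".
- Change: "Changes between baseline and follow-up will be analyzed by one-way ANOVA followed by" Tukey's test.
- Significance: a P value below 0.05 "will be considered to be statistically significant by using appropriate software".

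No measurement scale, transformation, distribution check, outlier rule or baseline adjustment is given. The change rule covers everything in the analyte list of the study description. That list runs from low-variation quantities such as albumin and calcium to "HDL-cholesterol, LDL-cholesterol, triglycerides, uric acid, creatinine", "insulin, osteocalcin, hematocrit, hs-CRP, TSH, FT3, FT4" and "gastric hormones (GIP, GLP1, GLP2, ghrelin, glucagon, PYY, CCK, leptin, resistin". Each participant has "two venous blood samples taken at the beginning of the observation and at the end", about 15 days apart, so a baseline value is available for every blood marker. The opening paragraph also makes urine and serum micronutrients a secondary outcome.

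**The concern.** Without a stated scale, the natural reading of change under ANOVA is follow-up minus baseline in the assay's own units. For a marker whose spread grows with its level, that difference is governed by the few participants with high values. A proportional effect of the lettuce is then diluted by their noise. Lipid and iron metabolism and gut hormones are named in the study's aim, so the markers most likely to be affected are central to it. What is at stake is missed effects and unstable estimates, using data the trial already plans to collect.

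**Working it through.** **Inputs from the document.** Two groups, two measurements per participant, 15 days, significance level 0.05 (taken as two-sided). There is no sample size, power, SD or correlation, so the plan has no figure of its own to reproduce.

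**Assumptions.** Log-normal marker with log-scale SD *s*; baseline to day-15 correlation ρ = 0.7; *n* = 20 or 40 per arm; a proportional effect with ratio exp(±3·*s*·√((1−ρ²)·2/*n*)). For *n* = 20 and *s* = 0.5: 3 × 0.5 × √(0.51 × 0.1) = 0.339, giving ratios of 1.40 and 0.71.

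**Analytic check of the log-scale columns.** Log change has noncentrality 3·√((1+ρ)/2) = 3·√0.85 = 2.77. With *n* = 20 the critical t is 2.02, so power is about Φ(0.74) = 77%. With *n* = 40 it is 1.99, giving about 78%. Log-scale ANCOVA has noncentrality 3, which gives at most Φ(3 − 1.96) = 85%.

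**Simulated power (20,000 trials per setting).** With two groups, ANOVA on change is the pooled t test.

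| n per arm | log-SD | true ratio | raw change | log change | log-scale ANCOVA |
|---|---|---|---|---|---|
| 20 | 0.2 | 0.87 / 1.15 | 73% / 77% | 77% / 76% | 82% / 82% |
| 20 | 0.5 | 0.71 / 1.40 | 60% / 74% | 77% / 77% | 82% / 82% |
| 20 | 1.0 | 0.51 / 1.97 | 36% / 56% | 77% / 77% | 82% / 82% |
| 40 | 0.5 | 0.79 / 1.27 | 63% / 74% | 78% / 78% | 84% / 84% |
| 40 | 1.0 | 0.62 / 1.61 | 40% / 55% | 78% / 78% | 84% / 83% |

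Decreases fare worse because equal log effects are unequal in raw units. At *s* = 1.0 and *n* = 20, ratio 0.51 is a 49% fall in the mean, while ratio 1.97 is a 97% rise.

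**Scale and adjustment separated.** ANCOVA on the original scale reaches only about 57% at log-SD 1.0, against 82-84% on the log scale. Baseline adjustment alone therefore does not close the gap.

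**Second set of assumptions.** Here *n* = 30 per arm, increases only, with the effect set for 80% power on log change. Raw-change power at correlation 0.5 / 0.8 is 81% / 80% at log-SD 0.2, 79% / 75% at 0.5, 71% / 64% at 0.8 and 63% / 55% at 1.0. In sample-size terms, power of 71% instead of 80% corresponds to (1.96 + 0.84)² / (1.96 + 0.55)² = 1.24, and 55% corresponds to (2.80)² / (1.96 + 0.12)² = 1.81. At log-SD 0.8 to 1.0 that is roughly 25-80% more participants for the same power.

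**Extreme values.** In a group of 30 with correlation 0.7, the largest single deviation holds a median 39% of the sum of squares of raw change at log-SD 1.0 and 25% at 0.5. On the log scale it holds about 18%.

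**Type I error.** Raw-change ANOVA rejects a true null in 3.7-4.9% of trials, so it is not inflated.

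**Cost of logging a marker that is really normal** (ANCOVA, 20 per arm). The loss is about 1-2 points at a CV of 20% or less. At a CV of 30%, power is 75-78% on the log scale against 82% on the original scale: 82 − 78 = 4 to 82 − 75 = 7 points (nearly 8 before rounding).

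**The case against.** The strongest case against has five parts.

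1. **The SAP never says raw scale.** True. A reader might infer that it prescribes untransformed differences. It prescribes ANOVA on changes and leaves the scale open, so arithmetic difference is the default reading. Either way the text needs a sentence.
2. **Extreme values do not create significant results.** True. A reader might infer that one high hs-CRP value could manufacture a group difference. It can shift the estimated difference, but it inflates the variance as well. With a single outlier of 5, 10 or 50 SD in one arm under the null (20 per arm), rejection is about 4%, 2% and 0%. The harm is masking. At log-SD 0.5 and 20 per arm, one day-15 value raised tenfold cuts raw-change power to about 10%, averaged over which arm it falls in; log-scale ANCOVA keeps about 51-53%.
3. **The loss comes from skew, not from being positive-only.** True. Albumin, calcium and total proteins are positive too, and at low variation they would lose next to nothing.
4. **Logging is not free.** True at larger CVs, as shown above. A fixed half-detection-limit substitution can also reverse the gain. At log-SD 0.5, 20 per arm and a true increase, log change falls to about 69% against 74% for raw change when 10% of baseline values are below the limit, and to 65% against 73% at 30%.
5. **The documents do not show which markers are skewed.** True. The named markers are an assumption, and the list needs the investigators' judgement.

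These points narrow the concern. They do not remove the loss on strongly skewed markers, which holds in both directions and at every sample size tried.

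**Conclusion.** The point stands as a recommended improvement to efficiency and robustness. The planned test remains valid as a test. On its plain reading it gives up about 3-17 points of power against log change at log-SD 0.5 (77 − 74 to 77 − 60) and about 21-41 points at log-SD 1.0 (77 − 56 to 77 − 36). At log-SD 0.2, raw change is about 3-4 points lower for a decrease and level for an increase. Log-scale ANCOVA adds roughly another 5 points over log change at correlation 0.7. All these figures rest on assumed log-normality, proportional effects, 20 to 40 per arm and correlation 0.7; none of these is in the documents. The documents do not support a wider claim that every positive marker should be logged or that the planned analysis produces excess false positives.

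**What to change.** Replace the sentence on changes with:

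> For every outcome, the day-15 value is compared between the two groups by ANCOVA adjusting for the baseline value. A list of markers expected to be strongly right-skewed, fixed before group data are seen and drawn from the urine and serum micronutrients as well as the blood markers (for example hs-CRP, ferritin, triglycerides, insulin, gut and adipose hormones), is analysed with both values log-transformed and reported as ratios of geometric means with 95% CI. All other outcomes are analysed by the same ANCOVA on the original scale.

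Add a sentence stating in advance how values below the detection limit are handled, with a sensitivity analysis for any marker where they are frequent. Tukey's test can go, since with two groups it adds nothing.

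For the blood markers this needs no extra participants or samples. For urine, a baseline sample must be confirmed, because the study description says only "collect plasma and urine samples after 15 days". Results for logged markers become ratios, and the list should hold only markers expected to be clearly skewed.

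### Forty-five outcomes are each judged at P < 0.05, with no primary outcome and no control across them, so a chance health effect is more likely than not

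*Combined protocol and SAP*

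**What the plan says.** The opening paragraph of the combined document sets the aim by domain: to "assess influence on hematological parameters and specific metabolism (glucose, lipid, iron, bone) and gut and lipid hormones". It then adds "Secondary outcome will be to find out micronutrient presence in urine and serum". That is the only outcome given a rank, and its micronutrients are not itemised.

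The design text that follows lists the measurements twice. The second time they are introduced as outcome measures: "The Outcome Measures will be Body weight, Barefoot standing height, Body mass index, Body composition by impedance analysis", followed by the full blood panel. No item is placed above another.

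The section headed Statistical analysis plan is three sentences long. Baseline characteristics are compared by t test, changes go to a one-way ANOVA with a Tukey follow-up, and "A $P < 0.05$ will be considered to be statistically significant". It sets no order of testing, makes no adjustment across outcomes and does not call the analyses exploratory.

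**The concern.** A 5% threshold limits the error of one test. Applied separately to dozens of outcomes, it leaves the chance of some false positive uncontrolled. Because no outcome is named in advance, a reader of the results could not tell a planned finding from the marker that happened to cross 0.05. The stated purpose is to look for benefits of the lettuce, so such a marker would naturally be presented as a health effect. At stake is whether any significant result from this trial can be taken as evidence.

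**Working it through.** The plan states no family-wise error rate, sample size or power, so there is no figure of its own to reproduce. The inputs are the threshold of 0.05 and the number of outcomes.

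**Counting the outcomes (from the outcome list)**

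- General chemistry, haematology and thyroid, from glucose to FT4 ("Samples will be analyzed and compared for glucose, albumin, total cholesterol, HDL-cholesterol, LDL-cholesterol, triglycerides, uric acid, creatinine, AST, ALT" and onward): 26.
- Bone and minerals ("Bone metabolism (Osteocalcin, parathyroid hormone, CTX, Calcitonin), Vitamin D Calcium, Phosphate, Potassium"): 8, of which osteocalcin and calcium are already among the 26.
- Gut and adipose hormones ("gastric hormones (GIP, GLP1, GLP2, ghrelin, glucagon, PYY, CCK, leptin, resistin"): 9.
- Blood entries: 26 + 8 + 9 = 43; distinct: 43 − 2 = 41.
- Weight, height, BMI and body composition: 4. Total distinct: 41 + 4 = 45.

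Urine and serum micronutrients, and any further impedance outputs, are not counted. Each would add tests.

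**Expected false positives if nothing has an effect:** k × 0.05. This does not depend on correlation.

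- 41 × 0.05 = 2.05
- 45 × 0.05 = 2.25

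**Chance of at least one, independent tests:** 1 − 0.95^k.

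- k = 41: 0.878
- k = 44 (height dropped): 0.895
- k = 45: 0.901

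For k = 45, the chance of two or more is 0.665 (binomial).

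**Chance of at least one, correlated tests.** The documents give no correlations, so the values below are assumptions. Results are from 200,000 simulated sets of 45 two-sided normal tests with no true effect.

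| Assumed correlation | P(at least one P < 0.05) |
|---|---|
| 0.1, all pairs | 0.88 |
| 0.3, all pairs | 0.78 |
| 0.5, all pairs | 0.60 |
| 0.7, all pairs | 0.39 |
| 0.8, all pairs | 0.29 |
| 0.5 within nine blocks of five, 0 between | 0.84 |
| 0.8 within nine blocks of five, 0 between | 0.71 |

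For the 41 analytes alone, the values at 0.3 and 0.5 are 0.75 and 0.58.

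**Does the Tukey step help?** It adjusts comparisons among group means for one outcome. The plan speaks of two groups, so on change scores there is one comparison per outcome and nothing to adjust. The ANOVA sentence could also mean four group-by-time cells with the pairing ignored. Simulating that with an assumed 15 or 30 per arm gives a per-outcome error of about 0.036 to 0.048. Over 44 independent outcomes the chance of at least one false positive is then about 0.80 to 0.89.

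**The case against.** There are four fair points on the other side.

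- **The 90% figure assumes independence.** Total and LDL cholesterol, AST and ALT, and weight and BMI plainly move together. This stands, and the range should be quoted with the figure. It does not rescue the rule. The chance falls below one half only if every pair of outcomes is correlated at roughly 0.6 or more, which is hard to argue for a panel running from TSH through ferritin to ghrelin. The expected count is unaffected.
- **The count is generous at the margin.** Height should not change in 15 days, and with height fixed BMI change largely repeats weight change. Dropping both leaves 43 outcomes and 1 − 0.95^43 = 0.890. The effect is small.
- **A main objective is implied.** The opening text puts haematological parameters first and returns to them. That is a domain, not a variable, and haematocrit is the only blood-count measure listed.
- **The study may be meant as exploratory.** Unadjusted estimates with intervals would then be defensible. But the plan does not say so, and it states a bare significance rule. Declaring the study exploratory would be a legitimate alternative, provided no result is then presented as confirmed.

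**Conclusion.** The concern holds and must be fixed. Following the stated rule exactly, with no true effect, about two outcomes would be expected to be declared significant. The chance of at least one is 88% to 90% under independence, 71% to 84% with correlated blocks, 75% to 78% with a common correlation of 0.3, and 58% to 60% at 0.5. Only strong correlation among all outcomes brings it below one half, and even at 0.8 throughout it is 29%, well above 5%. The expected count rests on the 45 named outcomes and a 5% error per test; the probabilities also rest on the assumed correlations. The uncounted micronutrient and impedance results would push the figures up.

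**What to change.** Before any data are analysed:

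1. Name one primary outcome from the first-stated aim and test it at two-sided 0.05. The choice is the sponsor's.
2. Label every other outcome secondary or exploratory, and apply Benjamini-Hochberg at a 5% false-discovery rate across them. Holm is the alternative, and it needs no assumption about correlation.
3. List the members of that family, including the individual micronutrients and impedance variables, so that it is fixed in advance.
4. Replace the significance sentence with this rule, and report an estimate with a 95% confidence interval for every outcome.
5. Measure standing height only to compute BMI; do not test it.

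The confirmatory claim then rests on the primary outcome, with a 5% false-positive rate. A false positive anywhere, in the primary test or in a separate 5% family, would have probability of about 1 − 0.95 × 0.95 = 0.0975 under no effect and independence, against 0.90 now.

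If data have already been examined, a primary outcome named now would not be confirmatory, and all results should be labelled exploratory.

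The cost is wording: the analysis plan, with matching edits to the aim and the outcome list. No sample, assay or participant changes. The price is that individual secondary markers need smaller p-values. With Holm, the smallest of 44 secondary p-values would have to be at or below 0.05/44 = 0.00114.
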